7.9 Interim Analyses

No interim analyses are planned.

7.10 Evaluation of Objectives

7.10.1 Primary Objectives

The primary objectives will compare the 95% CI of the AUC from the ROC curve to a value of 0.5 at 0-, 3-, and 6-months for the two definitions of PAD and one definition of CLI using the acceleration time from the FlowMet-R device. The 95% CI will not be corrected for repeated measures within a participant. If the 95% CI of the AUC excludes 0.5 at all time points for PAD or CLI, the acceleration time from the FlowMet-R device will be considered predictive of the respective endpoint. The 95% CI of the AUC will be derived using the method described in DeLong, et al (1998) [15]. Note, the definition of PAD will be defined two ways and analyzed separately. Definitions of PAD and CLI are provided in Section 4.1.1.1.1.

Three supplementary summaries will be computed. The sensitivity and specificity will be computed by selecting the point on the ROC curve closest to the upper left corner. Accuracy will be computed as the number of limbs correctly diagnosed divided by the total number of limbs.

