4.1.1.1.1 Definitions of PAD and CLI

- Two types of positive diagnosis of PAD will be explored according to published literature: (1) $ABI \leq 0.9$ or $ABI > 1.4$ and secondary verification of $TBI \leq 0.7$ with exhibition of at least mild claudication (Rutherford Category > 0), or (2) $ABI \leq 0.9$ or $ABI > 1.4$ and secondary verification of $TBI \leq 0.7$ without exhibition of symptoms. In either case, if the patient displays normal ABI but PAD is suspected, then a postexercise ABI will be performed using a 1-minute treadmill test or heel-raises. A postexercise drop of $ABI \geq 20\%$ or pressure drop $\geq 30\text{mmHg}$ will be considered a positive diagnosis [12].
- A positive diagnosis of CLI will be defined by exhibition of chronic rest pain and active wounds, verified by $TBI < 0.3$.
- Patients that are enrolled in the PAD positive cohort but are not positively diagnosed for PAD using the above definition (either because their disease is improving or they were screened incorrectly) will be considered PAD negative (see Section 7.11 for change to planned analysis).

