Subjects enrolled in the Healthy cohort will be assessed according to Event Schedule C in the CIP at a single time point. Imaging outside standard of care will not be performed on the healthy subjects, and healthy cohort subjects with normal ABI and TBI values will be assumed not to have significant peripheral arterial stenosis.

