5.1 Duration

The expected study duration is approximately 24-36 months. The duration of individual subject participation will vary based on timing of their enrollment and completion of the final follow-up visit; however, at a minimum, participation of an individual subject will be at least 6 months for subjects suspected of having PAD and 0 months for healthy subjects.

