7.1.3 Analysis Sets

Full Analysis Set

The full analysis set will include all participants and be used for all analyses. Visits outside of visit windows will be assigned to the nearest window. If a participant is missing data for a specific analysis, they will be excluded for that analysis. Within the analysis set, the grouping participants into the healthy, PAD (definitions 1 and 2), and CLI groups are defined in section 4.1.1.1.

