7.4 Handling of Missing, Unused, and Spurious Data and Dropouts

Data that is missing or incomplete will not be imputed. Complete case data will be used where all data for the respective analysis is available for a patient or visit.

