7.8 Acceleration Time Values

Acceleration time will be derived by the Research and Development Team based on data from the FlowMet device. Data should be merged based on the subject identifier, visit (0, 3, or 6 months), and limb.

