7.12 Changes to Planned Analysis

Patients will be classified based on definitions in Section 4.1.1.1.1 no matter the cohort they were originally enrolled in for the study.

8. Validation Requirements

To ensure the quality of the statistical results and datasets created for the study, the following validation requirements will be implemented. Programs that contribute directly or indirectly to the results pertaining to the primary and secondary objectives including TLG (Tables, Listings, and Graphs) development will be validated at least at level II by a statistician or a statistical programmer. Level I validation consists of a statistician or statistical programmer reviewer who independently programs output and then compares the output with that generated by the original statistician or statistical programmer according to the current work instruction. Level II: The peer reviewer reviews the code; where appropriate, performs manual calculations or simple programming checks to verify the output. Level III validation may be used for any previously validated program where only minor/administrative changes were made (e.g., change the location of the data directory). For level III validation, the original statistician or statistical programmer performs a visual inspection of the code and output to confirm functionality according to the current work instruction. Any results that are used for external publication or reports should be validated at levels I.

9. References

1. Mosely, L.H. and F. Finseth, Cigarette smoking: impairment of digital blood flow and wound healing in the hand. *The Hand*, 1977(2): p. 97-101.
2. Stadelmann, W.K., A.G. Digenis, and G.R. Tobin, Impediments to wound healing. *The American journal of surgery*, 1998. 176(2): p. 39S-47S.
3. Cronberg, C., et al., Peripheral arterial disease. *Acta Radiologica*, 2003. 44(1): p. 59-66.
4. Ouriel, K., Peripheral arterial disease. *The lancet*, 2001. 358(9289): p. 1257-1264.
5. Falanga, V., Wound healing and its impairment in the diabetic foot. *The lancet*, 2005. 366(9498): p. 1736-1743.
6. Norgren, L., et al., Inter-society consensus for the management of peripheral arterial disease (TASC II). *European Journal of Vascular and Endovascular Surgery*, 2007. 33(1): p. S1-S75.

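### The month-3 and month-6 AUCs in the all-visits rule contain no healthy controls, and the planned 0.8 is the power of one CLI curve, not of that rule

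*SAP*

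**What the plan says.** **Decision rule (SAP 7.10.1).** Acceleration time counts as predictive of PAD or CLI on this condition: "If the 95% CI of the AUC excludes 0.5 at all time points for PAD or CLI". The time points are months 0, 3 and 6. The section does not name the negative class for any curve. It also does not say which direction of acceleration time indicates disease.

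**Healthy cohort (SAP 5 and 5.1).** "Subjects enrolled in the Healthy cohort will be assessed according to Event Schedule C in the CIP at a single time point". Participation lasts "at least 6 months for subjects suspected of having PAD and 0 months for healthy subjects". Protocol 5 and 9.1 agree. Protocol 8.1 lists the 160 control limbs under Event Schedule A, but the matching list in SAP 5.3 drops that reference.

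**Data handling.** SAP 7.8: "Data should be merged based on the subject identifier, visit (0, 3, or 6 months), and limb". SAP 7.1.3: "If a participant is missing data for a specific analysis, they will be excluded for that analysis". SAP 7.4: "Data that is missing or incomplete will not be imputed".

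**Group assignment.** SAP 4.1.1.1.1 treats PAD-cohort patients who do not meet the PAD definition as PAD negative. SAP 7.12 adds: "Patients will be classified based on definitions in Section 4.1.1.1.1 no matter the cohort they were originally enrolled in for the study". SAP 7.1.3 speaks of healthy, PAD and CLI groups.

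**Sample size (SAP 6).** The planned quantity is the AUC of PAD groups against healthy controls, with alpha 0.05 and desired power 0.8. The pilot AUCs are 0.67 (claudication) and 0.80 (CLI), with tolerances of 0.05 and 0.2. The limb numbers are 160 control and 240 PAD, with at least 54 claudication and at least 100 CLI. Three visits, a joint rule and attrition are not mentioned.

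**The concern.** The rule requires three curves to pass, but they do not estimate the same thing. Month 0 includes healthy limbs. Months 3 and 6 can draw only on the PAD cohort. An AUC against healthy limbs and an AUC within a diseased cohort are different quantities, and the sample size addresses only the first.

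Three consequences follow. An analyst must choose the comparator at follow-up, possibly after seeing data. A follow-up pass or fail could be misread as PAD or CLI against healthy. The stated 0.8 could be taken as the chance of meeting the primary rule when it is not. In addition, a confidence interval wholly below 0.5 would also satisfy the rule as worded.

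**Working it through.** **1. Who is on the follow-up curves.** One healthy visit, a merge keyed on visit, no imputation and no carry-forward text leave no healthy value at month 3 or 6. SAP 4.1.1.1.1 with 7.12 points to all limbs not meeting the definition as negatives. The grouping in SAP 7.1.3, read with SAP 6, could instead suggest CLI against healthy, which cannot be computed at follow-up.

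**2. Formulas.** Let A be the AUC, n1 the positives and n0 the negatives, with limbs independent and a two-sided 0.05 level.

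- One-curve power = Φ((A − 0.5)/SE − 1.96).
- Hanley-McNeil (HM): SE² = [A(1−A) + (n1−1)(u−A²) + (n0−1)(v−A²)]/(n1·n0), with u = A/(2−A) and v = 2A²/(1+A).
- Binormal: SE² = 0.0099·exp(−a²/2)·[(5a²+8) + (a²+8)·n1/n0]/n1, with a = 1.414·Φ⁻¹(A).

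**3. The plan's own figure.** The lower planning AUCs are inferred: CLI 0.80 − 0.20 = 0.60; claudication 0.67 − 0.05 = 0.62.

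For CLI, 100 v 160, u−A² = 0.0686 and v−A² = 0.09. So SE² = (0.24 + 99×0.0686 + 159×0.09)/16000 = 0.001334, SE = 0.0365 and power = Φ(2.738 − 1.96) = 0.78.

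| One curve | AUC | HM | Binormal |
|---|---|---|---|
| CLI 100 v 160 | 0.60 | 0.78 | 0.80 |
| Claudication 54 v 160 | 0.62 | 0.75 | 0.78 |
| PAD 240 v 160 | 0.62 | 0.99 | 0.99 |

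Only the single CLI curve gives 0.8.

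**4. The three-visit CLI rule at AUC 0.60.** With 240 PAD limbs and 100 CLI, follow-up negatives are 240 − 100 = 140. HM power for 100 v 140 is 0.763 (SE 0.0374). With independent curves, joint power is 0.782 × 0.763² = 0.46.

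Month-0 and follow-up curves share positives but not negatives. The positives contribute (v−A²)/n1 = 0.0009 of variance, so their correlation cannot exceed 0.0009/(0.0365 × 0.0374) ≈ 0.66. Scaling shared components by an assumed within-limb correlation of 0, 0.5 and 0.8 gives joint power of about 0.46, 0.54 and 0.60. A DeLong simulation gave 0.45, 0.53 and 0.60.

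Other cases:
- All non-CLI limbs as month-0 negatives (160 + 140 = 300): one-curve power is 0.845, so the rule has 0.845 × 0.763² = 0.49 with independent curves and 0.59 at an equal correlation of 0.5 between curves.
- Floor of 54 non-CLI limbs, so 240 − 54 = 186 CLI: one-curve power is 0.911 (186 v 160) and 0.664 (186 v 54). The rule has 0.911 × 0.664² = 0.40 with independent curves and about 0.50 at an equal correlation of 0.5.
- Assumed 80% retention (80 v 112 at follow-up): 0.35 with independent curves.

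**5. How far the shortfall extends.** With 160 then 140 negatives and full retention, the rule reaches 0.8 at an AUC of about 0.62 to 0.63 at every visit. At 0.65 it has about 0.96.

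**6. PAD, illustrative only.** The documents give no count of follow-up negatives. If 12, 24 or 48 of 240 limbs were negative, power per follow-up curve at AUC 0.62 would be 0.35, 0.57 or 0.80 (HM).

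**The case against.** SAP 7.2 says the objectives are not hypothesis-driven and will be reported descriptively, and SAP 6 calls power desired and the numbers approximate. That lowers the stakes, but 7.10.1 still contains a pass rule and 6 still states a power. A descriptive label does not supply the missing negative class.

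The SAP names no variance formula, and 0.60 is an inferred reading of the 0.2 tolerance. Both points stand. The match to 0.8 is 0.78 or 0.80 depending on the formula.

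A visit that was never scheduled is not clearly missing data, and merge keys do not define a comparator. This also stands. A reader might infer that the SAP forbids reusing the healthy month-0 values at follow-up. It does not say so; it is silent. Reuse would, however, be a different analysis from the one written, and it would need to be stated.

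Protocol 8.1 could suggest that controls follow Schedule A. Protocol 5 and 9.1 and SAP 5 and 5.1 say otherwise, so it is a line to reconcile and does not supply follow-up controls.

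A reader might also pair the two minimums, 100 CLI and 54 non-CLI limbs, and obtain a much lower power. That makes 154 limbs, not the 240 planned.

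**Conclusion.** The point holds and should be fixed. As written, the follow-up curves are within-PAD-cohort contrasts that the sample size does not address, and 7.10.1 does not define their negatives. This part follows from the text and needs no assumption about power.

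The 0.8 describes one CLI-versus-healthy curve at AUC 0.60. The rule that decides the CLI objective has about 0.46 to 0.60 at that AUC with full retention, and about 0.40 to 0.50 at the coherent floor of 54 non-CLI limbs. These figures assume independent limbs, the planning AUC at every visit, unchanged CLI status and the stated correlations. The documents give no AUC for a within-cohort contrast.

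A reader might infer that the trial is underpowered for CLI in general. The documents do not support that: the shortfall is confined to the planning floor, and the pilot CLI AUC was 0.80. No firm power can be given for the PAD rule.

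**What to change.** 1. **SAP 7.10.1, negatives.** State that at each visit the negatives are all limbs measured at that visit that do not meet the definition in question, for each PAD definition and for CLI. State that healthy limbs contribute at month 0 only, and that positives and negatives are counted by cohort for every curve. Say whether a limb meeting only the other PAD definition is a negative or is left out. Interpret months 3 and 6 as within-PAD-cohort contrasts, separately from month 0.
2. **SAP 6, power.** Restate 0.8 as the power of one CLI-versus-healthy curve (100 v 160, AUC 0.60). Add the one-curve figures for claudication (0.75 to 0.78) and PAD (0.99). Give the lower power of the all-visits rule under stated counts, retention and correlation.
3. **SAP 7.10.1, direction.** Pre-state which direction of acceleration time indicates disease, and require the interval to lie above 0.5 in that direction.
4. **Tidying.** Reconcile the Schedule A reference in Protocol 8.1 with the single healthy visit. Correct the pointer in SAP 4.1.1.1.1 to Section 7.11, since the change is described in 7.12.

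The cost is SAP wording, one protocol clarification and a short recalculation. No new patients or visits are needed, and the three-time-point endpoint stays. The downsides are a less favourable stated power for CLI and follow-up curves that can no longer be presented as disease against healthy.

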12.1.2 FlowMet-R data analysis and diagnostic model

FlowMet-R data is comprised of continuous blood flow data recorded over 30 seconds. Over this time, a pulsatile blood flow waveform may be present due to the subject's cardiac cycle, provided that digital blood flow is sufficient to generate such a signal. Thus, a combination of the flow amplitude and one or more features of the waveform may be used as inputs to train the predictive model.

The target outcome variable for training the model shall be a continuous metric of PAD severity, analogous to the ABI or TBI. The training will be performed as a regression using iterative algorithms ubiquitous in machine learning.

The predicted outputs from the regression model will be used to generate an ROC curve by classifying a binary diagnostic (i.e. PAD true/false, CLI true/false), or prognostic (i.e. vascular intervention likely within 6 months (true/false)). The classification algorithm which results in the highest diagnostic area under the curve for PAD and CLI shall be chosen to compute final sensitivity and specificity.

A k-fold cross validation scheme will be implemented to gauge model generalization. k-fold cross validation is a statistical sampling method that can be used to train and objectively validate the above

classification algorithms [34]. Using this scheme, only a subset of the total body of collected data is used to train the model, which is then applied to the remaining data withheld from training prospectively. During this validation stage, the performance and generalizability of the model can be assessed. Cross validation allows more objective selection of the optimal algorithm because performance assessment is based upon applying the model to a data set which it is naïve to (i.e. a prospective application of the model).

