4.1.1.1 Primary Endpoints

Employ a predictive model based upon FlowMet-R data to generate ROC curves for the diagnosis of PAD and, independently, CLI. ROC curves will be generated at the initial, three month, and six month time points, and will be used to compute the peak sensitivity, peak specificity, and area under the curve (AUC).

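### Sensitivity, specificity and accuracy are read at a cut-off fitted to the same limbs with no optimism correction, so they will be modestly overstated; the AUC criterion is not touched by this

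*SAP*

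**What the plan says.** SAP 7.10.1 sets the operating point by one rule: "The sensitivity and specificity will be computed by selecting the point on the ROC curve closest to the upper left corner". It adds: "Accuracy will be computed as the number of limbs correctly diagnosed divided by the total number of limbs", without naming the cut-off that makes a limb count as correct. SAP 7.1.3 states: "The full analysis set will include all participants and be used for all analyses". The SAP has no separate set for choosing or testing a cut-off, and no resampling.

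The ROC curves are drawn "at 0-, 3-, and 6-months for the two definitions of PAD and one definition of CLI using the acceleration time". That is 3 visits × 3 definitions = up to nine curves. Nothing carries a cut-off from one curve to another.

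SAP 7.10.1 calls sensitivity, specificity and accuracy supplementary. SAP 4.1.1.1, like the same section of the protocol, puts the first two in the primary endpoint: the curves "will be used to compute the peak sensitivity, peak specificity, and area under the curve (AUC".

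Protocol 12.1.2 had a trained regression and a choice among classification algorithms. The algorithm with the best AUC "shall be chosen to compute final sensitivity and specificity", and "A k-fold cross validation scheme will be implemented to gauge model generalization". The SAP replaces the trained model by one feature, and in 7.8 states: "Acceleration time will be derived by the Research and Development Team based on data from the FlowMet device". SAP 7.12, which lists changes to the planned analysis, records only the regrouping of patients.

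**The concern.** A cut-off picked because it looks best in a sample fits that sample's noise as well as its signal. Sensitivity and specificity read on the same limbs are therefore biased upward for new patients. The protocol guarded against this by judging performance on data withheld from training, and the SAP has no substitute. Reducing the model to one feature removes the regression, but the cut-off is still a fitted quantity.

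What is at stake is the accuracy of figures named in the primary endpoint. SAP 5.2 presents sensitivity, specificity and accuracy as the demonstration of diagnostic capability. A 95% interval computed around the apparent value would be centred on the inflated figure.

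**Working it through.** The documents state no sensitivity, specificity, accuracy or threshold, so there is no figure of their own to reproduce. The check measures the bias that the SAP's rule produces at the plan's own AUCs and limb counts.

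**Inputs from the documents**
- AUC 0.67 (claudication) and 0.80 (CLI): SAP 6.
- 160 control limbs, 240 PAD limbs, at least 54 claudication and at least 100 CLI limbs: SAP 6.
- 400 limbs from a minimum of 250 patients: SAP 6.
- Healthy subjects are assessed once: SAP 5. PAD-negative limbs at 3 and 6 months can therefore come only from the PAD cohort.

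**Assumptions**
- Equal-variance normal scores: controls N(0,1), diseased N(d,1), with d = √2·Φ⁻¹(AUC).
- 20 to 40 PAD-negative limbs at follow-up against 200 positive. The documents give no count.

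**Formulas**
- True values at cut-off c: Se(c) = 1 − Φ(c − d) and Sp(c) = Φ(c).
- SAP rule: choose c to minimise (1 − Se)² + (1 − Sp)² on the observed limbs.
- Optimism = (apparent Se + Sp at c) − (true Se + Sp at the same c), averaged over several thousand simulated trials per setting.

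**Reference point.** For AUC 0.67, d = 1.414 × 0.440 = 0.622. The ideal corner cut-off is d/2 = 0.31, giving Se = Sp = Φ(0.31) ≈ 62%. For AUC 0.80, d = 1.414 × 0.842 = 1.190, the cut-off is 0.60 and Se = Sp ≈ 72%.

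**Results, in percentage points**

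| Limbs, diseased v negative | Sum Se + Sp overstated by | Average per measure (half the sum) |
|---|---|---|
| 240 v 160 | 2.5–3.3 | 1.3–1.7 |
| 100 v 160 | 3.4–3.9 | 1.7–2.0 |
| 54 v 160 | 4.8–5.2 | 2.4–2.6 |
| 200 v 20–40 (assumed follow-up) | about 5–9 | about 2.5–4.5 |

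In the last row at AUC 0.67, 40, 30 and 20 negatives give 2.9, 3.5 and 4.3 points per measure. Doubled, these are sums of 5.8, 7.0 and 8.6. The bias falls mainly on the measure estimated from the smaller group, so here nearly all of it is in specificity.

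Accuracy read at the same cut-off is overstated by about 1 to 2 points. This holds in the few-negatives setting too, because the larger group dominates the total. At the planned counts about three quarters of simulated trials overstate performance.

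**Does correction work?** Mean of sensitivity and specificity, from 800 runs, so differences can depart from the table by about 0.2:

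| Setting | Apparent | 10-fold cross-validated | True at chosen cut-off |
|---|---|---|---|
| AUC 0.67, 240 v 160 | 63.5% | 62.0% | 62.1% |
| AUC 0.67, 54 v 160 | 64.6% | 62.1% | 62.0% |
| AUC 0.80, 100 v 160 | 74.0% | 72.3% | 72.2% |
| AUC 0.67, 200 v 30 (assumed) | 65.3% | 61.9% | 61.9% |

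**Paired limbs.** If 250 patients give 400 limbs, 150 give two and 100 give one, so 300/400 = 75% of limbs are in pairs. With an assumed within-pair correlation of 0.6, average optimism per measure is 1.5 (240 v 160), 2.6 (54 v 160) and 1.8 (100 v 160), almost unchanged.

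**AUC.** For a score fixed in advance, the simulated mean AUCs were 0.670 and 0.800, with no optimism.

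**The case against.** The strongest reply is that the success criterion asks only whether the 95% CI of the AUC excludes 0.5, and no cut-off enters that. The SAP presents results descriptively, and the corner rule is prespecified, so nobody can hand-pick a threshold. The word peak in the endpoint itself suggests a best point on the observed curve. All of this stands. It limits the consequence but does not remove the bias from the reported figures.

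On cross-validation, Protocol 12.1.2 applies it to training and selecting algorithms and does not say that it covers the cut-off. With one feature, little of its target remains. That also stands: the omission matters for the cut-off only.

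The bias is also small beside sampling error, which is several points at these counts. True, but sampling error is expected and shown by an interval, whereas the bias runs in one direction and is not shown.

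A reader might infer more than the documents support:
- **Nine different cut-offs cannot yield a usable threshold.** No objective is to set a threshold, and choosing afresh for each curve is the natural reading rather than a stated rule.
- **Follow-up figures are certainly overstated by 5 to 9 points.** That rests on an assumed count and concerns PAD. For CLI, negatives may include PAD limbs without CLI, up to 240 − 100 = 140 if CLI sits at its minimum and follow-up is complete.
- **Acceleration time was tuned on this trial's data.** The documents do not say which data led to its choice. If they were this trial's, the AUC would be optimistic as well.

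**Conclusion.** The concern holds in a limited form. As written, 7.10.1 gives upward-biased sensitivity, specificity and, if read at the same cut-off, accuracy. The protocol's safeguard has gone without being listed as a change. At planned limb counts the bias averages about 1.3 to 2.6 points per measure and about 1 to 2 points for accuracy. It is larger for PAD at 3 and 6 months only if negatives are few there.

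These sizes rest on equal-variance normal scores, the plan's AUCs of 0.67 and 0.80, and the plan's limb counts. The AUC-based conclusion stands apart from this point, provided acceleration time was fixed before these data were used. The change is worth making because the affected figures are in the endpoint text and the correction is cheap; it does not put the primary criterion in doubt.

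**What to change.** In SAP 7.10.1:
- Report sensitivity, specificity and accuracy as 10-fold cross-validated or bootstrap optimism-corrected values. Resample by patient so that both limbs stay together. Show the uncorrected values alongside, labelled as apparent.
- State that accuracy uses the same cut-off as sensitivity and specificity.
- As an additional summary, apply each definition's baseline cut-off unchanged at 3 and 6 months. Note that negatives then come only from the PAD cohort, so case mix shifts together with threshold performance, and that these patients are not independent of baseline. This is not a validation and should not replace the corrected values.
- State on which data acceleration time was selected. If this trial's data were used, include that selection in the resampling, for the AUC as well.

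In SAP 7.12, list the removal of the protocol's k-fold scheme and the reason.

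The cost is SAP wording and a little programming, with no new data. The reported figures will be a few points less favourable.
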